5.8.3. Laboratory Evaluations

Results from the following laboratory parameters, recorded at their respective time points will be summarized by dose cohort and time point:

Hematology: (Screening, Days 1, 8 and 15 of each cycle, End of Treatment, Post Treatment Follow Up and End of Study).

RBC, WBC with differential, hemoglobin, hematocrit, haptoglobin (optional), reticulocyte count, platelet count, MCV, MCH, MCHC, RDW, and nRBCs

Chemistry: (Screening, Days 1 and 15 of Cycle 1, and Days 1 and 8 of each subsequent cycle, End of Treatment and End of Study).

Sodium, potassium, chloride, carbon dioxide/bicarbonate (optional), AST, ALT, lactate dehydrogenase (LDH), total bilirubin, indirect bilirubin, alkaline phosphatase, blood urea nitrogen (BUN)/urea, creatinine, GGT, calcium, phosphorus, glucose, amylase, lipase, total protein, albumin, and uric acid

Urine: (Day 1 of Cycles 1, 2 and 4, End of Treatment and End of Study).

PH, specific gravity, protein, glucose, ketones, blood, leukocyte esterase, and nitrite, with microscopic examination if indicated; Microalbumin and creatinine

Urine Chemistry: (Day 1 of Cycles 1, 2 and 4, End of Treatment and End of Study).

Microalbumin and creatinine will be performed by the central lab; individual and mean UACRs over time (for the ITT group) will be computed

Categorical and numeric variables will be presented separately.

Actual values and changes in hematology and biochemistry laboratory values from baseline will be summarize by dose cohort and by time point.

Shift tables for the hematology and biochemistry laboratory parameters comparing values above, within and below the normal reference range at baseline to the end of treatment visit will be presented using standard reference ranges.

Peripheral blood smears are taken at Screening, Day 1 of Cycles 1, 2, and 5 and at the end of treatment visit. These data will be listed only.

All laboratory values will be listed for all patients.

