In the three month monkey study, there was a dose dependent increase in BUN and creatinine. Histologic changes in the kidney consisted of membranoproliferative glomerulonephritis. This finding was dose dependent in both incidence and severity and was not sex dependent. At the highest dose (30 mg/kg), glomerulonephritis was accompanied by fibrosis and hemorrhage of the interstitium. The presence of immune complexes in renal tissue was demonstrated by immunohistochemistry and is suggestive of immune complex deposition; however, a direct effect of the drug cannot be excluded.

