### **12.3. Day 85**

- Day  $85 \pm 2$  days is the last possible study day that ACE-536 may be administered, regardless of the cycle.
- For expansion cohort 1 patients only, administration of quality of life questionnaires. Not required for expansion cohort 2 patients.

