## 14. ASSESSMENT OF SAFETY

### 14.1. Adverse Event Definitions

#### Adverse Event

An adverse event (AE) is any untoward medical occurrence in a patient or clinical investigation subject administered a study drug, which does not necessarily have a causal relationship with this treatment. An AE can therefore be any unfavorable and unintended sign (including an abnormal laboratory finding), symptom, or disease temporally associated with the use of the study drug whether or not it is considered related to the study drug.

Abnormal laboratory and other abnormal investigational findings (e.g. physical exam, ECG) should not be reported as AEs unless they are associated with clinical signs and symptoms, lead to treatment discontinuation or are otherwise considered clinically relevant by the investigator. In cases of surgical or diagnostic procedures, the condition/illness leading to such a procedure is considered as the AE rather than the procedure itself. In case of a fatality, the cause of death is considered as the AE, and the death is considered as its outcome.

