5. STATISTICAL METHODOLOGY

5.1. Definitions

Low Transfusion Burden (LTB)

LTB patients are defined as those who received < 4 units of RBCs within 8 weeks prior to Cycle 1 Day 1.

High Transfusion Burden (HTB)

HTB patients are defined as those who required ≥ 4 units of RBCs within 8 weeks prior to Cycle 1 Day 1.

Baseline Hemoglobin

Baseline hemoglobin will be an average of hemoglobin measurements within 28 days of Cycle 1 Day 1, excluding measurements within 7 days following RBC transfusion.

Baseline Transfusion Burden

Baseline transfusion burden will be calculated as the total amount of RBC transfusion during the 8 weeks prior to Cycle 1 day 1.

Baseline for Other Parameters

Baseline erythropoietin (EPO) is defined as the maximum test value within 28 days of Cycle 1 Day 1. For all other parameters, baseline is defined as the last observation on or prior to Cycle 1 Day 1.

End of Treatment (EOT)

Procedures and evaluations for the end of treatment visit should be performed on Day 113 (± 7 days) (28 days after the last dose of ACE-536).

Post Treatment Follow-Up (PTFU)

Procedures and evaluations for the post treatment follow-up visit should be performed on Day 141 (± 7 days) (28 days after EOT visit).

End of Study (EOS)

Procedures and evaluations for the end of study visit should be performed on Day 169 (± 7 days) (56 days after the Day 113/EOT visit).

Patients who discontinue treatment early should complete the end of treatment visit at the time of discontinuation and complete the post-treatment follow-up (PTFU) and EOS follow-up visits 28 days (± 7 days) and 56 days (± 7 days) after the EOT visit.

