5.14.4. Visit Windows

The following naming conventions for visit will be presented in the tables, listings and figures. The analysis window will be used for all safety assessments. For each patient, if more than one observation exists within the analysis window, an average value will be included in the analysis.

Visit	Abbreviated Visit	Visit window
Screening (Day -28)	Screen	28 Days prior to C1D1
Cycle 1 Day 1	C1 D1	Day 1
Cycle 1 Day 8	C1 D8	Day 8 ± 3 Day
Cycle 1 Day 11 ^a	C1 D11	Day 11 ± 3 Day
Cycle 1 Day 15	C1 D15	Day 15 ± 3 Day
Cycle 2 Day 1	C2 D1	Day 22 ± 3 Day
Cycle 2 Day 8	C2 D8	Day 29 ± 3 Day
Cycle 2 Day 15	C2 D15	Day 36 ± 3 Day
Cycle 3 Day 1	C3 D1	Day 43 ± 3 Day
Cycle 3 Day 8	C3 D8	Day 50 ± 3 Day
Cycle 3 Day 15	C3 D15	Day 57 ± 3 Day
Cycle 4 Day 1	C4 D1	Day 64 ± 3 Day
Cycle 4 Day 8	C4 D8	Day 71 ± 3 Day
Cycle 4 Day 15	C4 D15	Day 78 ± 3 Day
Cycle 5 Day 1	C5 D1	Day 85 ± 3 Day
Cycle 5 Day 8	C5 D8	Day 92 ± 3 Day
Cycle 5 Day 15	C5 D15	Day 99 ± 3 Day
End of Treatment	EOT	Day 113 ± 7 Day
Post-Treatment Follow Up	PTFU	Day 141 ± 7 Day
End of Study	EOS	Day 169 ± 7 Day

^a For PK data only.

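### Haematology and chemistry shift tables compare baseline only with the end-of-treatment visit, so no planned table counts patients whose on-treatment change had resolved by then and was not reported as an adverse event

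*SAP*

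**What the plan says.** SAP 5.8.3 specifies one set of shift tables for haematology and biochemistry, "comparing values above, within and below the normal reference range at baseline to the end of treatment visit". SAP 5.1 places the EOT visit: it "should be performed on Day 113 (± 7 days) (28 days after the last dose of ACE-536"). For early stoppers the rule differs: "Patients who discontinue treatment early should complete the end of treatment visit at the time of discontinuation".

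Haematology is sampled far more often than the shift table uses: "Screening, Days 1, 8 and 15 of each cycle, End of Treatment, Post Treatment Follow Up and End of Study". Chemistry is sampled at screening, Days 1 and 15 of Cycle 1, Days 1 and 8 of Cycles 2 to 5, EOT and end of study.

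The other laboratory outputs in SAP 5.8.3 are summaries by dose cohort and time point, and listings. SAP 5.2 makes minimum and maximum part of the default summary. SAP 5.14.4 adds that "if more than one observation exists within the analysis window, an average value will be included in the analysis", and applies its visit windows to all safety assessments.

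Protocol 14.1 says that abnormal laboratory findings "should not be reported as AEs unless they are associated with clinical signs and symptoms". The same sentence makes two exceptions: findings that lead to stopping treatment, and findings the investigator judges clinically relevant.

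**The concern.** A shift table is the laboratory output that ties a patient's abnormal value to that patient's baseline and counts how many patients changed category. Here it looks at one late visit. An abnormality that appears during dosing and has resolved by EOT is tabulated as if nothing had happened.

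Safety and tolerability is a secondary objective, and the protocol gives a reason to look at chemistry during dosing. In the three-month monkey study "there was a dose dependent increase in BUN and creatinine" (Protocol 7.2.2). A reader of the study report would want to know how many patients had creatinine move above range at any time after the first dose. The planned tables answer that only for EOT. The SAP is also uneven: ECG interpretation is categorised as improved, unchanged or deteriorated at each post-baseline visit (SAP 5.8.5), while haematology and chemistry have no by-visit or worst-value equivalent.

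**Working it through.** **Timing of the visit used.** Protocol 12.3 says that Day 85 ± 2 "is the last possible study day that ACE-536 may be administered, regardless of the cycle". Last scheduled dose plus 28 days: 85 + 28 = Day 113, which reproduces the SAP's figure.

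**Visits that enter the shift table (patient on schedule, Cycle 1 Day 1 as baseline; the Cycle 1 Day 11 visit is for pharmacokinetics only).**
- Haematology on treatment: 5 cycles × 3 visits − 1 = 14. Adding EOT, post-treatment follow-up and end of study gives 17. The table uses 1 of 17 (5.9%) and none of the 14.
- Chemistry on treatment: Cycle 1 Day 15 plus 4 cycles × 2 visits = 9. Adding EOT and end of study gives 11. The table uses 1 of 11 (9.1%) and none of the 9.
- Gap from the last on-treatment sample to EOT: haematology 113 − 99 = 14 days; chemistry 113 − 92 = 21 days.

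The percentages describe visit coverage. They are not the chance that an abnormality is missed, which depends on how long it lasts.

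**Early discontinuers.** The EOT analysis window is 113 − 7 = Day 106 to 113 + 7 = Day 120. Even an EOT visit made 28 days after a last dose on Day 1, 22, 43 or 64 falls on Day 29, 50, 71 or 92, all before Day 106. A visit made at discontinuation can be earlier still. The SAP does not say whether the shift table takes these values by visit name or drops them because of the window.

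**Averaging.** Consecutive on-treatment windows do not overlap: Day 8 + 3 = 11 and Day 15 − 3 = 12. Only repeats inside the same seven-day window are blended.

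**What each planned output can show for a transient on-treatment change in a completer.**

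| Output | Covers on-treatment visits | Counts affected patients |
|---|---|---|
| EOT shift (SAP 5.8.3) | No | Yes, at EOT only |
| By-visit summaries (SAP 5.2, 5.8.3) | Yes | No; cohort minimum and maximum only |
| Listings (SAP 5.8.3) | Yes | No; not tabulated |
| Adverse event tables (SAP 5.8.2) | Yes | Yes, if recorded as an adverse event |
| Dose delay and reduction counts (SAP 5.5) | Yes | Yes, but no breakdown by reason is specified |

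No row covers on-treatment visits and also counts patients whose change was not recorded as an adverse event.

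**The case against.** The strongest reply is that the safety signal would surface elsewhere. Much of this is right.
- By-visit minimum and maximum show an isolated extreme, and escalation cohorts have only 3 to 6 patients. That stands, subject to within-window averaging. But an extreme gives neither the number of patients affected nor their baseline category.
- Protocol 14.5 requires clinically relevant laboratory changes to be recorded as adverse events. A related non-haematologic event of Grade 3 or higher, which triggers a hold and reduction in Protocol Table 4, is by definition already an adverse event, counted per patient at its worst grade (SAP 5.8.2). That stands. The gap is therefore confined to changes not judged clinically relevant, not symptomatic and not leading to discontinuation.
- Early stoppers have EOT at discontinuation, so an abnormality that ends treatment may still be caught. That stands only if the window rule does not remove the value.
- The study is descriptive, the protocol asks for shift tables only as appropriate, and all values are listed. That limits the weight of the point but does not supply the missing count.

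Three stronger readings are tempting and are not supported.
- A reader might infer that a transient creatinine rise would appear in no summary at all. The by-visit extremes and the adverse event rules contradict this.
- A reader might infer that urine albumin is hidden in the same way. Urine is outside these shift tables, and SAP 5.8.3 plans individual and mean albumin-to-creatinine ratios over time.
- A reader might infer that EOT is a washed-out time point. A one-compartment model with the phase 1 time to peak (7.7 to 11.7 days) and half-life (15.5 to 18.5 days), and five equal doses 21 days apart, puts the level 28 days after the fifth dose at 0.78 to 1.25 times the first-dose peak. The point rests on using a single late visit, not on loss of exposure.

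**Conclusion.** The point holds as a reporting gap. For completers, the haematology and chemistry shift tables contain no on-treatment visit (0 of 14 and 0 of 9), and a change that resolves by EOT is classed as within range. No other planned table counts such patients unless the change was recorded as an adverse event. How many patients that would be cannot be estimated from the documents.

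This assumes five doses on schedule and the sampling in SAP 5.8.3. It also assumes that the adverse event rules in the supplied protocol carry into Amendment 06, on which the SAP is based; the supplied protocol text does not include expansion cohort 3. The primary endpoint and all efficacy results are unaffected. The change is a cheap improvement, not a correction of an invalid analysis.

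**What to change.** In SAP 5.8.3:
1. Add shift tables from baseline to the worst post-baseline value, with high and low directions in separate tables and CTCAE grade where one exists. Use individual unaveraged values, including unscheduled ones, so that the averaging rule in SAP 5.14.4 does not apply to these tables.
2. Keep the baseline-to-EOT shift and label it as a view of recovery.
3. State that EOT values of early discontinuers enter the EOT shift even when they fall outside Day 113 ± 7.
4. Optionally, count patients with WBC at or above 13,000/µL, creatinine above 2 × ULN, and (under SAP 5.8.4) systolic pressure at or above 150 or diastolic at or above 100 mm Hg. Label these as descriptive reporting cut-offs. The creatinine and blood-pressure values are eligibility limits in Protocol 9.3 and should not be presented as on-treatment safety rules.

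The cost is a few extra tables from data already collected. The downside is that a worst value taken over up to 17 or 11 scheduled visits, plus unscheduled ones, picks up more chance abnormalities than a single visit, so these tables should be read beside the EOT shift.

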### Diagnosis and Main Criteria for Eligibility

#### Inclusion Criteria:

1. Men or women  $\geq$  18 years of age.
2. Documented diagnosis of idiopathic/de novo MDS or non-proliferative chronic myelomonocytic leukemia (CMML) according to WHO criteria (white blood count [WBC]  $< 13,000/\mu\text{L}$ ) that meets International Prognostic Scoring System (IPSS) classification ([Appendix 2](#)) of low or intermediate-1 risk disease as determined by microscopic and standard cytogenetic analyses of the bone marrow and peripheral complete blood count (CBC) obtained during screening.
3. Anemia defined as:

- Mean hemoglobin concentration < 10.0 g/dL of 2 measurements (one performed within one day prior to Cycle 1 Day 1 and the other performed 7-28 days prior to Cycle 1 Day 1, not influenced by RBC transfusion within 7 days of measurement) for non-transfusion dependent patients (defined as having received < 4 units of RBCs within 8 weeks prior to Cycle 1 Day 1) (Participation in all cohorts), OR
- Transfusion dependent, defined as having received  $\geq$  4 units of RBCs within 8 weeks prior to Cycle 1 Day 1 (transfusion dependent patients are allowed in dose escalation cohorts and expansion cohort 1 only; patients with  $\leq$  6 units of RBCs within 8 weeks prior to Cycle 1 Day 1 may be allowed in cohort 2B).

4. Serum erythropoietin levels and prior erythropoiesis-stimulating agent (ESA) treatment:
  - Dose escalation cohorts and expansion cohort 1 patients: Serum erythropoietin level  $>$  500 U/L, OR, if  $\leq$  500 U/L, patient is non-responsive, refractory, or intolerant to erythropoiesis-stimulating agents (ESAs), or ESAs are contraindicated or unavailable.
  - Expansion cohort 2 patients: If patient is RS+ (defined as having  $\geq$  15% ring sideroblasts in the bone marrow), has less than 4 weeks' exposure to ESAs and serum erythropoietin level  $\leq$  200 U/L. If a patient is RS- (defined as having  $<$  15% ring sideroblasts in the bone marrow), prior ESA treatment and any serum erythropoietin level is allowed.
5. No alternative treatment options, per national MDS guidelines, are available and/or appropriate for the patient, at the discretion of the investigator.
6. ECOG performance status of 0, 1, or 2 (if related to anemia).
7. Adequate renal (creatinine  $\leq$  2 x upper limit of normal [ULN]) and hepatic (total bilirubin  $<$  2 x ULN and AST and ALT  $<$  3 x ULN) function.

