### 11.2. Clinical Laboratory Tests

The following laboratory assessments will be performed at the clinical site's local laboratory according to the laboratory collection recommendations. The sponsor may request additional safety tests be performed based on ongoing data review during the study.

- Hematology: RBC, WBC with differential, hemoglobin, hematocrit, reticulocyte count, platelet count, MCV, MCH, MCHC, and RDW.
- Serum chemistry: Sodium, potassium, AST, ALT, lactate dehydrogenase (LDH), total bilirubin, direct bilirubin, alkaline phosphatase, blood urea nitrogen (BUN)/urea, creatinine, GGT, calcium, phosphorus, glucose, amylase, lipase, total protein, albumin, and uric acid.
- Urinalysis by dipstick analysis: pH, specific gravity, protein, glucose, ketones, blood, leukocyte esterase, and nitrite, with microscopic examination if indicated.
- Pregnancy test: women of child bearing potential must have a negative pregnancy test at screening and prior to administration of ACE-536 on each dosing day.
- Screening visit only: serum folate and B12

The following laboratory assessments will be performed at the central laboratory according to the laboratory collection recommendations. The sponsor may request additional safety tests be performed based on ongoing data review during the study.

- Iron studies: Serum iron, TIBC, transferrin, soluble transferrin receptor, ferritin, NTBI and hepcidin.
- Nucleated RBC
- Erythropoietin levels
- Peripheral blood smear
- Urine microalbumin and creatinine
- Bone Biomarkers: serum BSAP and CTX (not collected for expansion cohort 2 patients).

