5.7.2.3. HI-N and HI-P Response Rate

Platelet (HI-P) and neutrophil (HI-N) response will be defined for patients with abnormal baseline values, following IWG 2006 criteria.

HI-P response will be defined for patients with baseline platelet count $< 100 \times 10^9/\text{L}$:

- For patients with baseline $\geq 20 \times 10^9/\text{L}$, an absolute mean increase of $\geq 30 \times 10^9/\text{L}$ during any rolling 8-week window on treatment;
- For patients with baseline $< 20 \times 10^9/\text{L}$, mean value of $> 20 \times 10^9/\text{L}$ and mean percentage increase $\geq 100\%$ during any rolling 8-week window on treatment.

HI-N response will be defined for patients with baseline neutrophil count (ANC) $< 1.0 \times 10^9/\text{L}$:

- Mean percentage increase $\geq 100\%$ and an absolute mean increase $> 0.5 \times 10^9/\text{L}$ during any rolling 8-week window on treatment compared with baseline.

The number and percentage of HI-N/HI-P responders will be estimated. The HI-N and HI-P response will also be listed for each patient.

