5.8.1. Dose Limiting Toxicities

A Dose-Limiting Toxicity (DLT) is defined as any of the following toxicities, at any dose level occurring within 28 days of the first administered dose:

- a. Treatment related serious adverse event (SAE) of Grade ≥ 3
- b. Treatment related non-hematologic adverse event (AE) of Grade ≥ 3
- c. Treatment related hematologic AE of Grade ≥ 4

Incidence rates of DLTs will be presented by dose cohort. Details of DLTs will be presented in listings.

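### Three-level laboratory shift tables cannot show further worsening in patients who enter already outside the normal range; add shifts to worst post-baseline CTCAE grade

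*SAP*

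**What the plan says.** SAP 5.8.3 defines the laboratory safety shift tables as "comparing values above, within and below the normal reference range at baseline to the end of treatment visit". That gives three levels and one post-baseline visit. The same section summarizes observed values and changes from baseline by dose cohort and time point, tracks UACR individually and as a mean, and lists every laboratory value. SAP 5.2 includes minimum and maximum in the default continuous summary.

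The entry criteria (Protocol synopsis, 9.3.1 and 9.3.2) determine where patients start:

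- **Hemoglobin.** Non-transfusion-dependent (NTD) patients, called low transfusion burden (LTB) in the SAP, need "Mean hemoglobin concentration < 10.0 g/dL of 2 measurements". The other route is "Transfusion dependent, defined as having received" at least 4 RBC units in the 8 weeks before Cycle 1 Day 1, with no hemoglobin limit.
- **Platelets and neutrophils.** Only platelets below 30 x 10^9/L are excluded, and no neutrophil minimum is set.
- **Chemistry.** Creatinine up to 2 x ULN, bilirubin below 2 x ULN, and AST and ALT below 3 x ULN are accepted.

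On AEs, Protocol 14.1 says abnormal laboratory findings "should not be reported as AEs unless they are associated with clinical signs and symptoms, lead to treatment discontinuation" or are judged clinically relevant by the investigator. SAP 5.8 applies CTCAE grading to AEs. No planned table grades laboratory values.

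**The concern.** A normal-range shift table works when most patients start within range, because moving out of range is then the signal. Here eligibility places some patients in an outer category from the start. For them, below-to-below or above-to-above covers everything from no change to severe deterioration, and only improvement (or an overshoot to the opposite side) can leave the diagonal.

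This matters because the trial compares ascending doses and uses grade as its severity scale elsewhere. The dose-limiting toxicity (DLT) definition, for example, includes "Treatment related hematologic AE of Grade ≥ 4". Protocol 7.2.2 and 7.4 report glomerulonephritis with raised BUN and creatinine in both rats and monkeys, so renal chemistry is of interest. At stake is whether a reader can see, cohort by cohort, how many patients' laboratory values became materially worse.

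**Working it through.** The plan states no figure on this point, so there is nothing to reproduce. The check applies the SAP's rule to values that the entry criteria allow.

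**Step 1: which starting positions are guaranteed or admitted.**

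- Hemoglobin below range is guaranteed for NTD/LTB patients, provided the local lower limit of normal (LLN) is at least 10.0 g/dL. It is not guaranteed for transfusion-dependent (TD) patients, called high transfusion burden (HTB) in the SAP.
- Low platelets are admitted and provided for. SAP 5.7.2.3 states "HI-P response will be defined for patients with baseline platelet count" below 100 x 10^9/L, and defines the neutrophil response for baseline counts below 1.0 x 10^9/L. Protocol Appendix 2 scores 2-3 cytopenias at 0.5, which is compatible with intermediate-1 risk.
- Creatinine, bilirubin and AST/ALT above ULN are admitted up to the stated multiples.

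**Step 2: apply the rule.** A value is below if less than LLN, above if greater than ULN, and otherwise within. The documents give no LLN, so it is varied as an assumption. The values are illustrations, not predictions.

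| Parameter | Baseline to later value | Limit used | Table cell |
|---|---|---|---|
| Hemoglobin, g/dL | 9.9 to 5.0 | LLN 10.0 to 13.5 | below to below |
| Hemoglobin, g/dL | 9.0 to 6.0 | LLN 10.0 to 13.5 | below to below |
| Platelets, x 10^9/L | 90 to 10 | LLN 100 to 150 | below to below |
| Platelets, x 10^9/L | 31 to 10 | LLN 100 to 150 | below to below |
| Creatinine, x ULN | 1.9 to 6 | ULN = 1 | above to above |
| Bilirubin, x ULN | 1.9 to 10 | ULN = 1 | above to above |
| ALT, x ULN | 2.9 to 20 | ULN = 1 | above to above |

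Every row falls on the diagonal, across the whole assumed LLN range.

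**Step 3: what the continuous summaries add.** One patient's change from a to b moves a cohort mean by (b - a)/n. For creatinine, b - a = 6 - 1.9 = 4.1 x ULN:

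- n = 30: 4.1/30 = 0.14 x ULN
- n = 25: 4.1/25 = 0.16 x ULN
- n = 6: 4.1/6 = 0.68 x ULN
- n = 3: 4.1/3 = 1.37 x ULN

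The mean dilutes a single case in an expansion cohort but not in an escalation cohort of 3-6. The maximum shows the most extreme case at any cohort size, but not how many there were. If the largest rise is 4.1 x ULN, the maximum change reads 4.1 whether one patient in 30 or five in 30 had it. The mean goes from 0.14 to 5 x 4.1/30 = 0.68 x ULN, and does not show how many patients contributed.

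**Step 4: the visit compared.** The shift ends at the end of treatment (EOT) visit, about 28 days after the last dose. A nadir or peak during treatment that had recovered by then would be missed even on a finer scale.

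**Step 5: a comparison within the SAP.** For ECGs, SAP 5.8.5 counts a move from abnormal but not clinically significant to clinically significant as deterioration. Worsening within the abnormal range is therefore visible there; the laboratory tables have no equivalent.

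**The case against.** The strongest reply is that nothing is lost. Minimum and maximum of values and changes are tabulated by cohort and visit, and one extreme value in a cohort of 3-6 is conspicuous. UACR adds renal information. Protocol 14.5 requires clinically relevant laboratory changes to be recorded as AEs, so many severe values should reach the Grade 3 or higher AE tables in SAP 5.8.2. The protocol asks only for shift tables as appropriate, and all summaries are descriptive.

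Most of this stands, and it limits the point. It does not supply a count: extremes show that at least one patient worsened, listings leave the counting to the reader, and AE capture depends on investigator judgement.

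A reader might infer more than the documents support:

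- **That severe laboratory worsening would go unseen.** It would not; the masking is confined to the shift tables.
- **That patients generally, or often, start outside the range.** Only NTD/LTB hemoglobin is guaranteed. For the other parameters the documents show admission, not frequency.
- **That DLT findings or dose escalation are compromised.** DLTs are graded AEs within 28 days, and under Protocol 10.7 the Safety Review Team sees laboratory results directly. Neither uses this table.
- **That no other categorical laboratory table exists.** SAP 5.7.2.5 plans a ferritin shift, and SAP 5.7.2.3 reports neutrophil and platelet response percentages. Neither shows worsening of the safety parameters at issue.

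**Conclusion.** The point holds as a limitation of one set of safety tables. For hemoglobin in NTD/LTB patients, the three-level table cannot show worsening in anyone. The same applies to each patient who enters with low platelets, low neutrophils, or creatinine, bilirubin or AST/ALT above ULN; that number cannot be derived from the documents. Other outputs give partial cover, but none counts patients per cohort whose laboratory values worsened by severity.

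This rests on two assumptions. The first is a local hemoglobin LLN of at least 10.0 g/dL. The second is that the entry limits above also apply to expansion cohort 3, which SAP 3.1 describes (9 patients treated) but the protocol text at hand does not.

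No estimate, decision rule or efficacy result is affected. It is a worthwhile, low-cost improvement to the safety presentation, not an error that undermines the analysis.

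**What to change.** Keep the three-level tables and supplement them in SAP 5.8.3:

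- **Add grade shifts.** Tabulate baseline CTCAE grade against worst post-baseline grade, by dose cohort, for hemoglobin, platelets, neutrophils, WBC, creatinine, bilirubin, AST and ALT. Add baseline to EOT if wished. Worst grade is needed because an EOT-only grade shift would still miss changes that had recovered.
- **Use the right limits.** Compute ULN-based grades from the reporting laboratory's own limits. Protocol 11.2 introduces hematology and serum chemistry with "The following laboratory assessments will be performed at the clinical site's local laboratory", so SAP 5.8.3's reference to standard reference ranges should be clarified to match.
- **Name one CTCAE version.** Protocol 10.6 and 14.3 specify v4.0; SAP 5.8 specifies v5.0, and SAP 5.15 does not list this as a change. Reconcile them against the protocol amendment on which the SAP is based, then state the version for both AEs and laboratory grades.

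The cost is a short SAP edit and routine programming on data already collected. Nothing changes for patients or sites. The only downside is a few more tables.
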